Statistical Analysis Plan

Study Title: The effects of PF-04995274 on emotional processing in treatment-resistant, medicated, depressed patients (RESTART study).

CT REGISTRATION: NCT03515733. ETHICS REF: 18/SC/0074

Objectives

The primary aim of the study is to investigate the effects of 7 days of PF-04995274 administration (adjunctive to SSRI/SNRI medication) on behavioural measures of non-emotional and emotional cognition, specifically memory performance on an auditory verbal learning task and performance (including accuracy and reaction times) on a facial expression recognition task. The secondary aim of the study is to investigate the effects of 7 days of PF-04995274 administration (adjunctive to SSRI/SNRI medication) on other behavioural measures of non-emotional and emotional cognition.

Brief summary of design

This study uses a double-blind, placebo-controlled, randomised between-groups design. Participants are patients who fulfil criteria for current episode of Major Depressive Disorder (MDD) and are currently taking an SSRI/SNRI and have failed to response clinically. Participants will be randomised to receive 7-9 days treatment with either PF-04995274 (15 mg daily) or a matched placebo. This study includes three visits in total: (a) Screening Visit; (b) First Dose Visit; (c) Research Visit Two. All visits will take place at the Warneford Hospital, Oxford University Department of Psychiatry.

Determination of Sample Size

We will recruit 50 participants to the study (25 on PF-0499574 and 25 on placebo). Participants who withdraw during the study or do not provide complete data-sets will be replaced. Based on data acquired in Harmer et al., (2004) comparing citalopram to placebo, if we aim for 0.9 power and a 0.05 false positive rate, a suggested group sample size is 19 (G*power) to ensure determination of group level differences at this variable if they exist. As 5HT4 agonism is less well studied, and to account for the exclusion of low quality data before analysis, we will aim for 25 individuals with complete datasets per group (total sample size of 50).

Data Cleaning

- Will be performed prior to unblinding
- Outliers will be excluded on a per task basis
- For all behavioural data, excluding the EPS, cut-off thresholds will be determined based on a visual inspection of a histogram plot, examining thresholds for:
 - > Trials with unusually low response times
 - > Trials with unusually high response times
 - Proportion of missing/removed trials per participant
 - Abnormally low mean accuracy (or equivalent outcome) per participant
 - Abnormally high mean reaction time per participant
- For all self-report data, extreme outliers indicating invalid data entry will be determined based on a visual inspection of a histogram plot
- For emotion potentiated startle data, two researchers will independently a) distinguish startle blink response from noise and decide whether a response could have been seen, had one occurred, excluding trials if no response could not be seen and b) determine if there is a blink response or if the trial should be recorded as a non-response. If there is disagreement, a third researcher will make a final decision.

Behavioural Analysis

Below is a non-exhaustive list of outcomes and analyses which will be conducted.

Behavioural Task	Outcomes	Analysis		
		 All key endpoints will be summarized (mean, standard deviation) in tables and bar charts (mean ±SEM) 		
		Conducted in R (version will be confirmed in publications)		
Facial Expression	Unbiased hit rate, as described by Wagner (1993) – a	Repeated measures analyses of variance (ANOVAs):		
Recognition Task (FERT)	measure of emotion identification accuracy which	Between-subject factor – 2 levels: Treatment group (PF-		
	accounts for response bias i.e. any general tendency to	04995274 or placebo)		
Recognition of computer-	identify the emotion when it is not present. Calculated as	Within-subject factor – 7 levels (Fear, anger, happy, surprise,		
based positive and negative	proportion of correct hits * (number of hits/all hits and	disgust, sad, neutral)		
facial expressions	misses), for each facial expression category.			
	% correct and response bias will also be reported			
P1vital® Limited Products	individually.			
	Misclassifications: Number of responses to each facial			
	expression category incorrectly classified as another facial			
	expression category e.g. identifying a fearful face as			
	surprised			
	Reaction time (ms) for trials with correct responses.			
Auditory Verbal Learning	Number of words recalled -	Repeated measures analyses of variance (ANOVAs):		
Task (AVLT)	List A immediate recall trials	 Between-subject factor – 2 levels: Treatment group (PF- 04995274 or placebo) 		
Recall of words read aloud		Within-subject factor - 5 levels (List A immediate recall trials 1-5)		

Pen and paper	Number of words recalled -	Repeated measures analyses of variance (ANOVAs):
	List A short delay	Between-subject factor – 2 levels: Treatment group (PF-
	Number of words recalled -	04995274 or placebo)
	List A long delay	Within-subject factor - 2 levels (List A short and long delay
		trials)
	Number of intrusions (words incorrectly recalled) across	Independent samples t-tests
	List A acquisition trials	
	Number of repetitions (words repeated within the same	
	trial) across List A acquisition trials	
	Number of words recalled -	
	List B recall	
	Number of hits and false alarms in the delayed	
	recognition test	
Probabilistic Instrumental	% Accuracy (correct or incorrect symbol choice)	Independent samples t-tests
Learning Task (PILT)	Correct = symbol associated with high probability of	
	winning or low probability of losing	
Reward sensitivity	Proportion of group choosing correct symbol per trial	The proportion will be calculated, and plotted on a learning curve
		to determine where learning plateaus.
Neurobehavioral Systems		
Presentation software		Repeated measures analyses of variance (ANOVAs) - trials where
(https://www.neurobs.com)		learning has plateaued
		Between-subject factor – 2 levels: Treatment group (PF-
		04995274 or placebo)
		 Within-subject factor – 2 levels: Condition (win or loss)
	Learning rate from reinforcement learning model	Repeated measures analyses of variance (ANOVAs)
		Between-subject factor – 2 levels: Treatment group (PF-
		04995274 or placebo)
		Within-subject factor – 2 levels: Condition (win or loss)

	Decision temperature parameters from reinforcement learning model	 Repeated measures analyses of variance (ANOVAs) Between-subject factor – 2 levels: Treatment group (PF-04995274 or placebo) Within-subject factor – 2 levels: Condition (win or loss)
	Amount won Amount lost Total monetary amount earned	Independent samples t-tests
Emotional Categorisation Task (ECAT) Categorisation of emotional words	% Accuracy – words correctly identified as positive or negative	 Mixed model analyses of variance (ANOVAs). Between-subject factor – 2 levels: Treatment group (PF-04995274 or placebo) Within-subject factor – 2 levels: Word valence (positive or negative)
P1vital® Limited Products Emotional Recall Task (EREC)	Reaction time Number of hits (words recalled correctly) Number of false alarms (words recalled incorrectly)	
Recall of emotional words from ECAT P1vital® Limited Products		
Emotional Recognition Task (EMEM)	Number of hits (words recognised correctly) Number of false alarms (words recognised incorrectly)	
Recognition of emotional words from ECAT	Reaction time	
P1vital [®] Limited Products		

Facial Dot Probe Task	Vigilance scores derived from reaction time – e.g. bias	Mixed models analyses of variance (ANOVAs).
(FDOT) Vigilance to fearful and happy faces P1vital® Limited Products	scores calculated by subtracting median reaction times in congruent trials (i.e. the probe appears behind the emotional expression) from those in incongruent trials (i.e. the probe appears behind the neutral expression)	 Between-subject factor – 2 levels: Treatment group (PF-04995274 or placebo) Within-subject factors 2 levels: Emotion (positive or negative) 2 levels: Probe duration (masked or unmasked)
Emotion Potentiated	Raw amplitude of startle response	Mixed models analyses of variance (ANOVAs).
Startle (EPS)	Raw amplitude of startle response	Between-subject factor – 2 levels: Treatment group (PF- 04995274 or placebo)
EMG data, in response to white noise during positive or negative images	Z-transformed amplitude of startle response	 Within-subject factors – 2 levels: Trial type (positive, negative, neutral)
San Diego Instruments, San Diego, CA, USA	Latency of startle response (ms)	
Oxford Memory Test (OMT)	Proportion of correct probe selections	Mixed models analyses of variance (ANOVAs). Between-subject factor – 2 levels: Treatment group (PF-
Visual short term spatial memory	Absolute error for probe location Reaction Time	 04995274 or placebo) Within-subject factors – 2 levels: Trial condition (1 or 3 memory probes)
Oxford Memory Test application "Short_Fractals1" — modified from "What was where task" (Pertzov et al., 2013) running on iOS 12.3.1		

Self-report or researcher-observed scale – all completed on Qualtrics.XM (https://www.qualtrics.com) except HAM-D			
Eysenck Personality Questionnaire (EPQ)	Total score for each dimension	Report descriptives for each group	
State and Trait Anxiety Inventory –	Total score		
Trait subscale (STAI-T)			
Becks Depression Inventory (BDI)	Total score		
Hamilton Depression Scale (HAM-D)	Total score		
Pen and paper – scored by research team			
Snaith-Hamilton Pleasure Scale (SHAPS)	Total score		
State and Trait Anxiety Inventory –	Total score	Mixed model ANOVAs:	
State subscale (STAI-S)		Between-subject factor – 2 levels: Treatment group (PF-04995274 or	
Positive and Negative Affect Scale	Total score for positive and negative	placebo)	
(PANAS)	subscales	• Within-subject factors – 4 levels: Time condition (Pre-scan, Post-scan,	
Visual Analogue Scales (VAS)	Total score for each VAS (happy, sad, hostile, alert, anxious, calm)	Pre-ETB, Post-ETB)	
Side effects	Presence of side effect Severity of side effect Belief in relationship to drug	Descriptive report of frequency of side-effects for each group at four time points (baseline, pre-dose, post-dose and all other study days combined).	
		A generalised linear model will be used to analyse side effects, with presence of side-effect as outcome and predictors including treatment group (PF-04995274 or placebo) and time point (baseline, pre-dose, post-dose, day 2/3/4/5/6/7/8/9).	
		For side effects significantly associated with group and time-point, we will investigate severity and belief in relationship to study drug.	

When conducting ANOVAs, the Greenhouse-Geisser procedure will be used to correct the degrees of freedom where assumptions of equality of variance are violated. If there is a significant group x condition interaction found in ANOVAs. Post hoc independent samples t tests will be performed to follow up any significant interactions. We will not use the Bonferroni correction for multiple comparisons for post-hoc tests. When conducting t tests, degrees of freedom will be corrected where the assumption of equal variances between groups is violated (i.e. Levene's Test is significant).

Record of version changes and unblinding

Date	Version	Blinding Status	Comments
28 th October 2022	1.0	Team blinded, barring unblinding for study medics (AdeC, PC and BG) where necessary.	Data collection complete. First version of complete stats plans. Uploaded to clinicaltrials.gov and OSF.

Study Team involved in analysis

AdeC - [name] [name] - DPhil Student, Study Medic

AG - [name] – Post-doctoral Researcher

BG - [name] - Study Medic

CH - [name] - Principal Investigator

MB - [name] - Research Assistant

PC - [name] – Principal Investigator, Study Medic

SM - [name] - Senior Research Fellow

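### The primary aim spans several FERT and AVLT outcomes with none designated primary and no error control across them, so the stated 0.9 power and 0.05 rate cannot be read as properties of that aim

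*SAP*

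**What the plan says.** Under Objectives, the SAP's primary aim concerns cognition, "specifically memory performance on an auditory verbal learning task and performance (including accuracy and reaction times) on a facial expression recognition task". That is two tasks, and for the FERT at least two kinds of measure.

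Under Determination of Sample Size, citing an earlier comparison of citalopram with placebo, it says "if we aim for 0.9 power and a 0.05 false positive rate, a suggested group sample size is 19 (G*power"), and gives the purpose as "to ensure determination of group level differences at this variable if they exist". No variable is named before or after that phrase. The 19 is then raised to 25 per group.

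The table under Behavioural Analysis is introduced with "Below is a non-exhaustive list of outcomes and analyses which will be conducted". For the FERT it lists unbiased hit rate, misclassifications and reaction time, each with a group by seven-expression ANOVA. Percentage "correct and response bias will also be reported" individually. For the AVLT it lists two ANOVAs (immediate recall trials; short and long delay) and t tests on intrusions, repetitions, List B recall and "Number of hits and false alarms in the delayed" recognition test. No row is marked primary.

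After the table, the only statements that bear on multiplicity are "Post hoc independent samples t tests will be performed to follow up any significant interactions" and "We will not use the Bonferroni correction for multiple comparisons for post-hoc tests".

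**The concern.** A primary aim accompanied by a power and a false positive rate invites the reader to attach those two figures to the aim. Here they belong to one unidentified variable, while the aim can be answered by several group comparisons. Nothing in the SAP says which of them decides the aim, or how several are to be judged together. A significant result on any one FERT or AVLT measure could then be presented as the answer to the primary aim, at an error rate that the plan neither states nor limits. A reader of the publication could not tell a planned primary result from one picked out of many.

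**Working it through.** **Inputs from the SAP:** power 0.9, false positive rate 0.05, 19 per group, 25 per group planned. **Not given in the SAP:** the variable, effect size, SD, test, sidedness, a significance threshold for the analyses, and any correlation between outcomes. Below, each test is read at 0.05, and correlations are assumed over the range 0.3 to 0.9.

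**1. The plan's own figure.** The 19 cannot be reproduced forward, because no effect size is given. It can be solved backward with the two-sample t test: power = 1 − F(t_crit; df = 2n − 2, noncentrality d√(n/2)). Setting n = 19 and power = 0.9 gives d = 1.08 if two-sided, or d = 0.97 if one-sided. This does not show the 19 to be wrong; it only gives the effect that the 19 implies.

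**2. How many tests can answer the primary aim.**
- One contrast per task: 2.
- Narrow reading (FERT unbiased hit rate and reaction time; AVLT immediate and delayed recall): 4.
- Wide reading, one test per listed outcome: FERT 3 + AVLT 2 ANOVAs + AVLT 5 t tests = 10. Misclassifications count once; recognition hits and false alarms count as two.
- Adding the group x condition term of each ANOVA: FERT 3 × 2 + AVLT 2 × 2 + 5 = 15.
- If percentage correct and response bias are tested rather than only described: 12 outcome-level tests, or 5 × 2 + 2 × 2 + 5 = 19 with interactions.

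**3. Chance of at least one false positive under the complete null.** Under independence it is 1 − 0.95^k. The correlated ranges for 4 and 10 tests run from a common r of 0.9 across all tests (lowest) to r = 0.3 within task only (highest).

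| Tests k | Independent | Assumed r from 0.9 to 0.3 |
|---|---|---|
| 2 | 9.8% | – |
| 4 | 18.5% | about 9-18% |
| 10 | 40.1% | about 13-37% |
| 12 | 46.0% | 22-43% (within task only) |
| 15 | 53.7% | 35-52% (within task only) |
| 19 | 62.3% | 37-60% (within task only) |

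The last three ranges come from simulating the listed t and F tests with 25 per group and the two tasks uncorrelated. For 15 and 19 tests they span two assumptions about whether FERT interactions correlate across outcomes. A common correlation across tasks would lower them: at r = 0.9, 19 exchangeable tests give about 15%. The post hoc t tests add nothing to these figures, because under the complete null each one needs a significant interaction first.

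**4. With Holm.** For two independent contrasts, the chance of any false positive is 1 − 0.975² = 4.9%. Power at 25 per group (df = 48) for a variable with the implied effect, two-sided, at the strictest Holm step:

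| Contrasts | Alpha at first step | d = 1.08 | d = 0.97 |
|---|---|---|---|
| 1 (no correction) | 0.05 | 0.96 | 0.92 |
| 2 | 0.025 | 0.93 | 0.86 |
| 3 | 0.0167 | 0.91 | 0.82 |
| 4 | 0.0125 | 0.88 | 0.79 |

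Holm's power lies between the first-step value and the uncorrected one, depending on how the other tests turn out.

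**The case against.** Several points on the other side are fair.

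- The protocol is not at hand and may name the powered variable and a primary endpoint. A reader might infer that the variable was never specified anywhere. The documents do not support that; they show only that this SAP's sentence points to nothing within the SAP.
- A reader might infer that the plan puts 10 to 19 tests behind its primary aim. That is the wide reading. The aim speaks of memory performance and of FERT accuracy and reaction times, so whether intrusions, repetitions or misclassifications answer it is a judgement. The upper counts also require testing percentage correct and response bias, which the SAP says only will be reported. Four outcomes is a defensible count.
- Outcomes within a task are correlated, so the independence figures are upper illustrations. With strong correlation across everything, ten tests give about 13%, not 40%.
- A reader might infer that the SAP refuses correction across outcomes. It does not. It declines Bonferroni for post hoc tests, which already depend on a significant interaction, and is silent on the rest.
- The SAP makes no family-wise claim, and 0.05 appears only as a sample-size input. In a 50-patient study of cognitive tasks, strict control is partly a matter of choice. But the SAP does not call the study exploratory; it declares a primary aim and supports it with a power calculation.

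These points reduce the size of the problem and leave its core: several eligible outcomes, no ranking, an open list and no rule across them.

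**Conclusion.** The point holds. On this SAP alone, the primary aim can be met by any of several uncorrected tests, and the stated 0.9 and 0.05 do not describe it. The chance of at least one false positive is 9.8% with a single independent test per task. It is about 9-18% on the narrow reading of four outcomes, and 13-40% on the wide reading of ten, taking in correlations from 0.9 down to none. It rises further if interactions, percentage correct and response bias are also tested. Every reading tried exceeds 5%. The figures rest on three assumptions: each test at 0.05, the complete null, and assumed correlations.

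Two stronger conclusions are not supported: that 19 or 25 per group is too few, since the calculation cannot be checked without an effect size; and that anyone choosing outcomes knew the allocations, since the SAP records only that study medics were unblinded where necessary. The correction is worth making because it is textual and still possible before the analysis is unblinded.

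**What to change.** Before unblinding, and decided only by team members who have not been unblinded:

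1. Name one primary contrast for the FERT and one for the AVLT. Each may be a group main effect or a specified group x condition contrast; the planned ANOVAs allow either. Apply Holm across the two at an overall two-sided 0.05.
2. If the sponsor wants both FERT accuracy and FERT reaction time to stay primary, include each in the Holm family.
3. Label all other FERT and AVLT analyses, the post hoc tests and any analysis not listed as secondary or exploratory.
4. Identify the variable used for the sample size, and state that the 0.9 power applies to that variable only.

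**Cost.** No patients or data are added. The primary claim becomes narrower, and with only one FERT contrast either accuracy or reaction time moves to secondary. For a variable with the effect implied by 19 per group, power at 25 per group is at least 0.93 (two-sided reading of the 19) or 0.86 (one-sided reading) with two contrasts, and at least 0.88 or 0.79 with four. Power for any other outcome is unknown, because the SAP gives no effect size. The version record says data collection was complete at version 1.0, and study medics are on the analysis team list, so any medic who was unblinded must stay out of the choice.

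### The formula printed for the FERT unbiased hit rate has no false-alarm term, so on its plain reading it is the squared hit rate and corrects no response bias

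*SAP*

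**What the plan says.** The Objectives section of the SAP puts "performance (including accuracy and reaction times) on a facial expression recognition task" in the primary aim, beside verbal memory.

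In the Behavioural Analysis table, the first outcome in the FERT row is the unbiased hit rate, attributed to a 1993 publication. The cell says the score "accounts for response bias i.e. any general tendency to" report an emotion that is absent. The calculation follows as "proportion of correct hits * (number of hits/all hits and" and, on the next line, "misses), for each facial expression category". The cell adds that % "correct and response bias will also be reported" individually. Misclassifications and reaction time are listed as further outcomes. No other formula for the unbiased hit rate appears in the SAP, and none is given for response bias.

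**The concern.** Reporting an emotion when it is not there is a false alarm. A score that adjusts for this must change when the number of false alarms changes. The printed formula uses only hits and misses, and both are counted on faces that do show the emotion. Responses to all other faces are left out.

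If an analyst programs the formula as printed, the score carries the same information as % correct under a name that claims more. A treatment that merely makes patients choose one label more often, for example 'happy', raises the hits on happy faces. It could then be reported as better recognition after adjustment for bias, which is the misreading the score is meant to prevent.

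**Working it through.** **Inputs.** The formula and its purpose come from the FERT row of the SAP. The seven emotion categories, 25 participants per group and the order of testing are also in the SAP. It gives no number of faces, hit rates or variances, so those below are assumed.

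**Algebra.** For one emotion let H be hits, M misses (faces of that emotion given another label), F false alarms (other faces given this label), and N = H + M the faces of that emotion shown.

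- Printed formula, plain reading: (H/N) × H/(H + M) = (H/N)².
- Formula with false alarms: (H/N) × H/(H + F).
- The two agree (for H > 0) only when F = M, that is, when the label is used exactly as often as the emotion is shown. In that case there is no bias to correct.

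**Worked example** (assumed N = 20, H = 12, so M = 8 and H/N = 0.60). The largest possible F is 6 other emotions × 20 faces = 120.

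| F | Printed formula | With false alarms |
|---|---|---|
| 0 | 0.36 | 0.60 × 12/12 = 0.60 |
| 3 | 0.36 | 0.60 × 12/15 = 0.48 |
| 8 | 0.36 | 0.60 × 12/20 = 0.36 |
| 18 | 0.36 | 0.60 × 12/30 = 0.24 |
| 120 | 0.36 | 0.60 × 12/132 = 0.055 |

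An extreme case: a participant who calls every face fearful (7 categories, 10 faces each, assumed) scores (10/10) × (10/10) = 1.00 on fear by the printed formula. With false alarms the score is (10/10) × (10/70) = 0.143.

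**Effect on the planned test.** The SAP runs a group by emotion ANOVA with Greenhouse-Geisser correction. Its condition for follow-up t-tests is: "If there is a significant group x condition interaction found in ANOVAs". This sequence was simulated with a softmax response model, 25 per arm, 20 faces per emotion, baseline hit rates of 0.51 to 0.61 and 2,000 trials per cell. The drug had no effect on sensitivity and only shifted bias towards one label. The table shows how often the printed score falsely showed improvement on that label.

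| Between-person SD in logits (bias, sensitivity) | Shift 0.3 | Shift 0.5 | Shift 0.7 |
|---|---|---|---|
| 0.2, 0 | 28% | 80% | 98.5% |
| 0.5, 0 | 12% | 40% | 76% |
| 0.2, 0.5 | 11% | 44% | 79% |
| 0.5, 0.5 | 8% | 26% | 55% |
| 1.0, 0 | 4% | 13% | 27% |
| 1.0, 0.5 | 4% | 10% | 21% |

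Over the same settings the score with false alarms gave 0.5–1.8%, 0.7–2.5% and 0.8–4.0% at the three shifts. With no shift the printed score gave 0.3–0.7%. Plain % correct behaves almost like the printed score: 8%, 23% and 51% at SDs of 0.5 and 0.5.

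Separately written code, run at three of these settings with 1,000 trials per cell, gave similar results. For the printed score these were 30/82/99% (SDs 0.2, 0), 8/28/61% (0.5, 0.5) and 4/10/22% (1.0, 0.5). The score with false alarms reached at most 4.2%.

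**The case against.** The strongest reply is that the SAP fixes the measure by name, citation and stated purpose before it gives the formula, so a competent analyst would compute the right score. The two factors are also worded differently, which is an odd way to write a square. If the first factor means the share of uses of a label that were correct, H/(H + F), the product is H/(H + F) × H/(H + M), which is exactly the score with false alarms. This makes a slip of wording likely. It does not make the printed text correct: the SAP never states that reading, and its word-recall and word-recognition rows use 'hits' for correct responses.

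Alternatively, 'misses' might be loose wording for false alarms. The SAP has that term and uses it for other tasks, for example "Number of hits and false alarms in the delayed" recognition test. Those are word-memory tasks and the FERT row speaks of misclassifications, so this argues against the loose reading without excluding it.

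Third, % correct, response bias and misclassifications are reported as well, and a pure labelling shift should show there. That stands as a safeguard for an alert reader, but it does not correct the score itself. Nor does the SAP rank the unbiased hit rate above the other FERT outcomes; it is only listed first.

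Finally, the simulated error rates apply only if the code follows the printed formula and the drug shifts bias without changing sensitivity. That is true, and the wide range shows how far they depend on assumptions.

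**Conclusion.** The concern holds. On its plain reading, the formula for an accuracy outcome within the primary aim is a monotone transform of % correct and cannot do what the same cell says it does. That conclusion is algebra and needs no assumption about the data.

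The possible harm is conditional. If the code follows the text and the drug shifts labelling by 0.3 to 0.7 logits, false improvement appears in 4% to 98.5% of simulated trials, against roughly 4% at most for the score with false alarms. The shift sizes, between-person spreads, response model and face counts are all assumed. Nothing in the SAP shows that the analysis was programmed wrongly. But as the text stands, an analysis faithful to the formula lacks the claimed adjustment, and a correct analysis departs from the publicly posted plan.

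**What to change.** Replace the formula with explicit numerators and denominators, for each emotion: (hits / number of faces of that emotion shown) × (hits / all uses of that label, that is, hits plus false alarms). State what value is assigned when a participant never uses a label, because the second denominator is then zero. Check that the analysis code matches. Enter the change in the SAP's record of version changes with its date and the blinding status at that time. If the code already computes this score, only the wording changes.

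The cost is one line of text and a check of one line of code. The response counts needed are already required for the misclassification outcome, and there is no effect on patients or timelines.

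### The side-effect model treats 9–11 repeated yes/no reports per participant as independent, and its follow-up trigger does not target a post-dose difference between arms, so it can err in either direction

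*SAP*

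**What the plan says.** In the SAP's Behavioural Analysis section, the side-effects row has three parts.

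- **Description:** "Descriptive report of frequency of side-effects for each group at four time points (baseline, pre-dose, post-dose and all other study days combined"). This does not depend on any test.
- **Model:** "A generalised linear model will be used to analyse side effects, with presence of side-effect as outcome and predictors including treatment group" "and time point (baseline, pre-dose, post-dose, day 2/3/4/5/6/7/8/9").
- **Follow-up rule:** "For side effects significantly associated with group and time-point, we will investigate severity and belief in relationship to study drug".

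The row names no participant term and no group-by-time interaction. The Brief summary of design says "Participants will be randomised to receive 7-9 days treatment", so the number of daily reports varies between people.

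Two other places bear on the reading. The section opens with "Below is a non-exhaustive list of outcomes and analyses which will be conducted". The mood and anxiety scales, which are also repeated self-reports, do get a declared repeated factor: "Within-subject factors – 4 levels: Time condition (Pre-scan, Post-scan" and two further occasions.

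**The concern.** There are two separate faults.

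1. **Repeated reports.** A person who tends to have headaches will report them on several days. A plain logistic model counts each report as a new independent observation. Treatment varies only between people, so the standard error of the group effect comes out too small and its p-value overstates the evidence.

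2. **The trigger.** The phrase linking group and time point could mean that both main effects are significant or that their interaction is. For main effects, it does not say whether time is judged by one omnibus test or by any single time coefficient. A group main effect averages over baseline and pre-dose, when no drug has been taken. A time main effect averages over arms. An interaction on all 11 levels spreads a post-dose shift over 10 degrees of freedom. None of these is the direct question: do the arms differ after dosing, given where each participant started?

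At stake is which symptoms have severity and perceived drug relationship examined, and the credibility of any group p-value reported from this model.

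**Working it through.** **Stated figure.** The SAP gives no error rate, event rate or power for side effects, so there is nothing to reproduce.

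**Reports per person.** Baseline, pre-dose and post-dose make 3. Days 2–7 add 6 and days 2–9 add 8. Hence 3 + 6 = 9 to 3 + 8 = 11.

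**Approximate effect on the group test.** With T reports and within-person correlation ICC, the design effect is DE = 1 + (T − 1) × ICC, and the real error of a nominal two-sided 5% test is 2 × [1 − Φ(1.96/√DE)]. For T = 11 and ICC = 0.3, DE = 1 + 10 × 0.3 = 4, and 2 × [1 − Φ(0.98)] = 0.33. Over ICC 0.1 / 0.2 / 0.3 / 0.5:

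- T = 9: 0.14 / 0.22 / 0.29 / 0.38
- T = 11: 0.17 / 0.26 / 0.33 / 0.42

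**Simulation.** From the SAP: 25 per arm, and 11 reports of which 2 are pre-drug. Assumed, because the SAP gives none: two-sided 0.05 for this model, average pre-drug prevalence of 20% or 5%, random-intercept SD of 1 or 2 on the logit scale, a drug effect of 1.2 log-odds after dosing, and common post-dose rises of 0.7 or 1.35 log-odds. For scale, a move from 10% to 30% is ln(0.3/0.7) − ln(0.1/0.9) = 1.35. The model is logistic with group and time as factors and no participant term. Results are from 1,000 trials per setting unless marked.

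| Scenario and rule | 20%, SD 1 | 20%, SD 2 | 5%, SD 1 | 5%, SD 2 |
|---|---|---|---|---|
| No drug effect: group test rejects | 17% | 37% | 10% | 26% |
| Drug-only rise: both terms, omnibus time test | 17% | 2% | 11% | 2% |
| Drug-only rise: both terms, any time coefficient | 61% | 24% | 19% | 6% |
| Drug-only rise: interaction, 10 df | 16% | 3% | 13% | 5% |
| Drug-only rise: pooled post-dose contrast (a) | 91% | 58% | 66% | 30% |
| Placebo rise 0.7, drug a further 1.2: both terms, omnibus | 87% | 33% | 47% (b) | 11% (b) |
| Equal rise 1.35, no drug effect: both terms, omnibus | 22% | 14% | – | – |

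(a) Post-dose reports pooled, adjusted for the pre-drug count, independence GEE with Mancl–DeRouen variance and t on 47 df; 2,000 trials. Its null rejection was 2.8–4.6% over SD 0.5–2. (b) 600 trials.

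Repeat runs gave similar figures:

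- Group test: 19% / 38% / 12% / 23% across the four columns.
- Drug-only omnibus rule at 20% prevalence: 16–21% (SD 1) and 2–3% (SD 2).
- Equal rise of 1.35 at 20% prevalence: 20–21% and 15–16%. At 10% prevalence it was 12–14.5% and 9%.

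With SD 0 and no drug effect the group test rejected in 4.2–5.2%, so clustering is the cause of the inflation.

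**Second check, set by average rates** (9 and 11 reports, 400 trials, SD 1–2, both terms with omnibus time test):

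- Drug 10% to 30%, or 5% to 20%, with placebo flat: flagged 30–34% (SD 1) and 15–23% (SD 2), so 66–85% missed.
- Drug 10% to 40%, placebo 10% to 20%: flagged 81–90%.
- Both arms 10% to 30%, no drug effect: flagged 17–18% (SD 1) and 25–33% (SD 2).

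The interaction reading flagged only 4–23% in the first two scenarios.

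**Sparse symptoms.** At 5% prevalence, 48–59% of simulated trials (SD 0.5–2) had at least one time point with no events in either arm, so an 11-level time factor is unstable there.

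**The case against.** **The wording is open.** The predictor list is introduced as inclusive and the table as non-exhaustive, so a participant term is unspecified rather than ruled out. That is fair, but it does not rescue the model. Extra predictors are covariates; a random effect or GEE is a different model, and the one named is a plain generalised linear model.

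**The rule mainly misses drug-related symptoms.** A reader might infer this from the drug-only rows. The documents do not support it as a general statement, because they do not say how placebo symptoms behave or which reading applies. When placebo also rises by 0.7, the omnibus rule catches 87% at 20% prevalence and SD 1. Even with placebo flat, the any-coefficient reading catches 61% there. The missing participant term on its own pushes the group test towards false positives.

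**False flags arise only if any single time coefficient counts.** A reader might infer this too. It is true for a modest common rise: at 0.7 log-odds the omnibus rule flags at most 4.3%. It fails for larger rises, as the 1.35 row shows.

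**The interaction does compare the arms over time.** This stands. Its fault is low power on 10 df, not irrelevance.

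**The consequence is small.** This also stands. Side effects are not among the Objectives, frequencies per arm are tabulated whatever the model shows, and a wrong flag changes only the look at severity and belief.

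**Conclusion.** Wrong as written, with modest impact. The missing allowance for repeated reports is clear from the text. Its direction for the group test is also clear: false group signals at roughly 10–38% instead of 5% in the settings assumed.

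That the trigger is ambiguous and poorly aimed is equally clear, but the direction of its error is not fixed. It depends on the reading chosen, on how placebo symptoms move after dosing, and on prevalence and within-person correlation. The exact percentages rest on assumed prevalence, SD and effect sizes; the SAP supplies only the arm size, the time points and the treatment length.

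**What to change.** Replace the plain model with one named method, for example a logistic GEE clustered on participant with Mancl–DeRouen variance.

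Make one contrast the sole trigger for the severity and belief follow-up: the group effect on pooled post-dose reports, adjusted for presence of the symptom at baseline and pre-dose. Pooling suits the data, since the descriptive summary already combines the later days and days 8–9 exist only for some participants.

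Name one fallback for sparse symptoms, such as a permutation test of the same contrast (null rejection 3.4–5.4% in simulation). State in advance the cut-off that invokes it, for instance a minimum number of participants with a post-dose report, so that the choice of test does not follow the results.

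Version 1.0 records data collection as complete and the team as blinded, apart from study medics where necessary. Date the change before unblinding, or report it as a disclosed change if unblinding has occurred.

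Cost: a few lines of SAP text, a different model call, wider intervals for the group effect and slightly more analysis work. No new data are needed.
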